Primary Outcome	Rate of space closure	Digital scanned dental models	
- Scanned digital models in (mm)
○ Models taken every month○ Analysed using 3 Shape Software

Secondary Outcome	Anchorage loss	Digital scanned dental models	Linear measurement in scanned digital models (mm)
	Molar Rotation	Digital scanned dental models	Degrees
	Vertical position	Lateral Cephalometric Xray	Mm
	Torque of anterior teeth	Lateral Cephalometric Xray	Degrees
	Pain	Pain scoring sheets given to patients	VAS scoring from 1-10 ^(Fig 1)

B-Research question:

In orthodontic patients with maxillary protrusion, can frictionless mechanics offer a faster rate of retraction compared to frictional mechanics?

Objectives of the study

Research hypothesis:

The null hypothesis (H_0) of this research is that there's no difference between both frictionless and friction mechanics on rate of retraction during en-masse retraction following 1st premolar extraction.

Primary objective:

Evaluating the rate of En-masse retraction using frictionless vs friction mechanics.

Secondary objectives:

Assessing the amount of anchorage loss, root resorption, pain and discomfort during retraction. In addition to this, changes in vertical position (extrusion/ intrusion), tip and torque of anterior teeth will be measured following en-masse retraction using frictionless vs friction mechanics.

Study design:

This is a randomized clinical trial with two arms parallel group, and 1:1 allocation ratio. In one group, frictionless mechanics will be applied during en-masse retraction, while the other group will receive frictional mechanics. The rate of retraction will then be compared between both interventions.

Material and Methods

I) Participants, Interventions, and Outcomes

A] Study Setting:

The study will be performed in the clinic of the Orthodontic Department at the Faculty of Oral and Dental Medicine, Future University. The recruited sample would be from the Egyptian urban and rural population.

B] Eligibility criteria:

- Inclusion criteria:** for the participants include the following:
 1. Adults and Adolescent patients (both genders)
 2. Age range (14-24)
 3. Patients with maxillary protrusion requiring first premolars extraction (Bimaxillary Protrusion or Class II division 1 cases).
 4. Patients with fully erupted permanent teeth (not necessarily including the third molar).
 5. Cases requiring maximum anchorage during retraction.

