 6. Good general and oral health

- Exclusion Criteria:** for the involved subjects included:
 1. Patients suffering from any systemic diseases interfering with tooth movement.
 2. Patients with extracted or missing permanent teeth. (except for third molars).
 3. Patients with badly decayed teeth.
 4. Patients with any parafunctional habits (i.e. Bruxism, tongue thrusting, mouth breathing, etc...).
 5. Patients with previous orthodontic treatment

C] Interventions:

➤ **Medical History Questionnaire:**

For every patient, to exclude the presence of any systemic condition interfering with orthodontic treatment.

➤ **Clinical Examination:**

Oral structures will be examined to identify caries, fracture or missing teeth. Gingival tissues will be carefully examined for any gingivitis, periodontitis, recession, or lesions.

➤ **Diagnosis**

Check the potential patient to fulfill the previously mentioned inclusion criteria. Every participant will be asked to sign an informed consent about the study. Full set of records (study models, panorama radiograph and lateral cephalometric radiographs, photos) will be taken for every patient as part of the routine procedure for treatment of patients in the clinic of the Orthodontic Department, Future University.

➤ **Clinical Procedure:**

After taking pre-treatment records, every patient will receive:

- Bonding of all teeth except for first premolars and banding/bonding the first and second molars will be done using Roth prescription brackets (0.022 x 0.028 slot)*.
- Miniscrews** will then be placed in the upper arch between the second premolar and first molar.

*American Orthodontics

** Jeil Miniscrews

- The patient will be referred for extraction of first premolars.
- Anchorage will be secured, followed by Leveling and alignment for the bonded and banded teeth through following the wire sequence: 0.014 NiTi, 0.016×0.022 NiTi and 0.017×0.025 StSt.
- After levelling and aligning is completed (right before retraction), the patient will be referred for the uptake of pre-intervention records.

➤ **Acquisition of pre-intervention records:**

- The patient will be referred for the uptake of a Lateral Cephalometric radiograph, which will be considered the T0 record.
- Impressions will be taken before retraction (without the archwire in place) followed by digital scanning of produced models.

➤ **Begin of Retraction:**

Frictionless group:

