- A ligature wire extended between the second premolars and miniscrews will be used for proper anchorage control.
- Closing retraction T-loops will be fabricated using 0.017 x 0.025 TMA wire. The loop will be positioned halfway the extraction space and the canine.^{35,36}.
- A gable angle of 45° will be added.
- Distal activation of 4 mm will be done with cinch back the wire distal to 2nd molars bilaterally.³⁷

Friction group:

- Crimpable hooks added to the arch wire (0.017"x0.025" Stainless steel) distal to the lateral incisor passing near the center of resistance of the anterior segment.
- Retraction will start on a 0.017"x0.025" Stainless steel wire using elastomeric chain (force applied will be 212 g per side)³⁸ extending between the crimpable hooks and the miniscrew.
- The force will be measured by a force gauge and reactivated every 4 weeks maintaining constant force of retraction all over the retraction phase.

➤ **Follow up visits**

Patients will be asked to attend for follow up sessions every 4 weeks for:

- Evaluation miniscrews stability.
- Replacement of the power chain to maintain a force of 212 gm per side.
- Reactivation of the T-loop by further distal activation and cinch back.
- Impression taking to determine the overall rate of retraction.

➤ **Criteria for discontinuing or modifying the allocated intervention:**

In cases of prolonged swelling or pain related to the miniscrew, the patient will be given strict oral hygiene measures and may wait for three weeks before the beginning of retraction.

In cases of loose or broken miniscrews, the screw will be removed and replace the miniscrew after complete resolution of the inflammation.

□ **Post-retraction Questionnaire:**

The patients of both groups will be asked to fill in questionnaires regarding their experience with their allocated technique

□ **Retraction records**

Following en-masse, patients will be referred to the same radiology center to acquire the final lateral cephalometric x-ray to assess the movement and inclination of anterior teeth.

The final dental model will assess the rate of retraction, molar rotation, and molar anchorage loss achieved throughout the study.

□ **Material Used**

- American Orthodontics Brackets, Roth prescription, 22 slot size.
- American Orthodontics Elastomeric power chains
- American Orthodontics Elastomeric O-ties
- American Orthodontics Ligature wire.

- Jiel Miniscrew, 8 mm TAD
- American Orthodontics Arch wires.

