- American Orthodontics Molar bands/tubes.

D] Outcomes

[figure not shown]
Primary outcome: is to monitor the rate of space closure during en-masse retraction. All outcomes will be assessed as the difference between T0 at the start of retraction and T1 after complete space closure.

Secondary outcomes: is to monitor the changes in the anterior teeth position (torque and vertical position), molar rotation, anchorage loss, and pain associated with the different methods used for retraction.

E] Participant timeline:

1. The principle investigator will screen the potential patients through careful clinical examination of patients at the orthodontic department, Faculty of Oral and Dental Medicine, Future University.
2. All recruited patients should fulfil the previously mentioned inclusion and exclusion criteria.
3. Every participant will be asked to sign an informed consent before the beginning of the study.
4. After patient's enrolment, each participant will be asked for pre-intervention records to ensure proper diagnosis.

5. The principle investigator will randomly allocate the patients to one of the intervention groups.
6. Anchorage will be secured by placement of miniscrew, followed by extraction of the first premolar.
7. Active intervention will begin after proper levelling and alignment of the upper arch.
8. The principle investigator will take pre-retraction records for every participant T0.
9. In Friction mechanics group, Power chain is used for anterior segment retraction while in Frictionless group, T-loop is used for retraction.
10. Each patient will come every 4 weeks for follow up visit, for appliance activation and uptake of impression for interim records.
11. After complete space closure, the principle investigator will take post-retraction records for each participant T1.
12. Every patient will fill up a questionnaire regarding his experience during treatment.
13. The principle investigator will continue the normal treatment and achieve proper finishing for every patient after the end of the study.

E] Sample size calculation:

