Our sample size calculation is based on a previous study comparing the effect of friction and frictionless mechanics²⁴. Using PS software output, we are planning a study of a continuous response variable from independent Group I and Group II subjects with 1 Group I(s) per Group II subject. In a previous study the response within each subject group was normally distributed with standard deviation 0.76. If the true difference in the Group II and Group I means is 1.0, we will need to study 10 Group II subjects and 10 Group I subjects to be able to reject the null hypothesis that the population means of the Group II and Group I are equal with probability (power) 0.8. The Type I error probability associated with this test of this null hypothesis is 0.05. Considering drop out a sample size 15 per group is appropriate.

F] Recruitment strategy:

The principal investigator will recruit the patients from the clinic of Orthodontic department, Faculty of Oral and Dental Medicine - Future University.

Screening of patients will continue until the total number of participants for the study is collected.

II) Assignment of interventions:

A] Sequence generation:

The supervisor of the study will apply Computer generated random numbers to randomly assign patients to group A (Frictionless) or B (friction) using Microsoft Office Excel 2007 sheet. The patient numbers will be written in the first column, and the supervisor will select function RAND() to generate the randomization number in the second column. These numbers will be sorted according to the randomization number so the first column numbers will be randomly distributed.

B] Allocation concealment mechanism:

The supervisor of the study will write the randomization numbers of the patients on opaque white papers folded three times to form sealed envelopes and store it inside a box. The codes for randomization will be securely held at the secretary's office.

C] Implementation:

At the time of intervention, the main operator will send the patient to the secretary's office. Then, the assigned employee will open the box and ask the patient to select one envelope. The main operator will assign each participant for the corresponding intervention either (friction or frictionless group) according to the list of codes of randomization.

Assignment to either intervention will occur before levelling and alignment stage.

D] Blinding:

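### The primary outcome is a rate, but the Outcomes section assesses it as a T0–T1 difference without time; no rate formula is given, and the arms are compared with a paired test

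*Combined protocol and SAP*

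**What the plan says.** All references are to the combined protocol and SAP.

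- **D] Outcomes.** The rate of space closure is primary. The next sentence reads: "All outcomes will be assessed as the difference between T0 at the start of retraction and T1 after complete space closure". One figure in this section is not shown in the text available.
- **Outcome measure table.** The primary outcome is in mm, with "Models taken every month". No time unit or formula is given.
- **C] Interventions, pre-intervention records.** "Impressions will be taken before retraction (without the archwire in place) followed by digital scanning of produced models". This is the baseline model.
- **C] Interventions, Follow up visits.** Every 4 weeks: "Impression taking to determine the overall rate of retraction".
- **C] Interventions, Retraction records.** "The final dental model will assess the rate of retraction, molar rotation, and molar anchorage loss achieved throughout the study".
- **III) A] Data collection methods.** The retraction rate is read on monthly models from before, during and after retraction. Anchorage loss, molar rotation, torque and vertical position use records from before and after retraction only. Pain comes from a questionnaire.
- **III) C] Statistical Analysis.** Item 2 uses a paired t-test both between the two arms and for pre-post change within each arm. Item 3 uses an ANOVA for the rate of anterior segment retraction and states neither response nor factors.
- **E] Sample size calculation.** Independent groups, SD 0.76, 80% power, alpha 0.05: "If the true difference in the Group II and Group I means is 1.0", 10 per group are needed. Then: "Considering drop out a sample size 15 per group is appropriate". Neither 1.0 nor 0.76 has a unit.

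**The concern.** The research question is which mechanics retract faster. A speed needs a distance and a time. The sentence that says how outcomes are assessed supplies only a distance, and it fixes the end of that distance at complete closure. It also gives the interim models no role, although other sections collect them for the rate.

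If the sentence is followed, the primary comparison is not one of speed. If it is set aside, the formula and the distance remain open and could be chosen after the data are seen. Total distance over total time, a slope, and a month-by-month comparison are different analyses. Space closure and anterior movement are different distances whenever the molars move. The one test named for comparing the arms does not fit the design either.

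**Working it through.** **1. Residual space.** Let S0 and S1 be the space at T0 and T1. Complete closure means S1 = 0, so S0 − S1 = S0 at any speed. With an assumed S0 of 6 mm:

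| Visits to closure | T0–T1 change | Rate per 4 weeks |
|---|---|---|
| 6 | 6 mm | 6/6 = 1.0 mm |
| 10 | 6 mm | 6/10 = 0.6 mm |

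This is an identity. Simulating a t-test on S0 in two randomised arms rejects about 5% of the time whatever the true rates, which only restates alpha.

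**2. Anterior movement.** Let M be forward molar movement. If the space closes by these two movements alone, anterior movement is S0 − M. Arms can then differ at T1 through M, but time is still absent. Illustration with assumed values (SD of S0 0.8 mm, SD of M 0.5 mm, independent): SD of S0 − M = √(0.64 + 0.25) = 0.94 mm. With 15 per arm, a between-arm difference in M of 0.5 or 1.0 mm is detected with about 29% or 80% power. That would be a finding about anchorage.

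**3. The sections side by side.**

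| Section | Timing of models for the rate | Distance |
|---|---|---|
| Outcome measure table | monthly | space closure |
| D] Outcomes | T0 and T1 | space closure |
| Follow up visits | every 4 weeks | retraction |
| Retraction records | final model | retraction |
| III) A] | monthly: before, during, after | anterior teeth and first molars |
| III) C] item 3 | not stated | anterior segment |

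No readable section gives a quantity per unit time.

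**4. Test between arms.** The study design is parallel with 1:1 allocation, and the sample size calculation assumes independent groups. No matching of patients is described, so a paired test would depend on an arbitrary ordering and could not use everyone if the arms ended unequal. With 15 per arm it has 15 − 1 = 14 degrees of freedom, against 2 × 15 − 2 = 28 for the independent-samples test.

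**5. Power basis.** Plan's figure, two-sided normal formula: n = 2(1.960 + 0.842)² × 0.76²/1.0² = 9.07, rounded up to 10, as stated. The noncentral t gives power 0.795 at 10 per arm. With 15 per arm the standardised difference detectable at 80% power is 1.0598:

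| SD of rate, mm per 4 weeks | Detectable difference |
|---|---|
| 0.76 (only if the plan's SD is a rate SD) | 0.81 |
| 0.15 (assumed) | 0.16 |
| 0.25 (assumed) | 0.26 |
| 0.40 (assumed) | 0.42 |

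So the stated 80% power cannot be tied to the rate without a unit.

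**6. Choice of formula.** Dividing by whole visits to closure understates the rate when closure falls between visits. In simulation (15 per arm; assumed starting space 5–7 mm with SD 0.5–1.2, rate SD 0.15–0.40), a true difference of 0.30 mm per 4 weeks (1.0 v 0.7) reads 0.25–0.27, and a true 1.0 (2.0 v 1.0) reads 0.75–0.83. A per-patient slope over models with space still open (space 6 mm, SD 0.8, assumed measurement SD 0.3 mm) recovers 0.29–0.30 and 0.99–1.00. At 1.0 v 0.7 its power is about 99.7%, 88% and 50% for rate SD 0.15, 0.25 and 0.40.

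**The case against.** The strongest reply is that III) A] is the more specific section and already makes the right split: serial models for the rate, and before-and-after records for anchorage loss, molar rotation, torque and vertical position. The outcome is called a rate throughout, visits are every 4 weeks, and T0 and T1 can be dated, so the Outcomes sentence may only describe the observation window. It cannot be literally true of pain. The missing figure might also bear on the definition.

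Much of this stands. A reader might infer that the trial has no data on speed, or that nothing in the plan governs the rate apart from the T0–T1 sentence. The documents do not support either, because the serial models are planned and assigned to the rate. A reader might also infer that the T0–T1 value must equal the starting space however it is measured. That holds for residual space only, as step 2 shows.

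What the reply does not supply is a formula, a time unit or a single distance. Nor does it remove the conflict: the Outcomes sentence says all outcomes, directly after naming the primary, and the Retraction records text also assigns the rate to the final model. Item 3 of the analysis mentions the rate but does not define it. None of this bears on the paired test.

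**Conclusion.** The concern holds in this form: the T0–T1 rule for all outcomes contradicts the serial measurement planned for the primary, and read literally it yields a quantity without time. In addition, no readable text defines the rate, the distance is inconsistent, and item 2 names the wrong kind of test for independent arms. This should be corrected before the data are analysed, because it concerns the primary outcome and the trial's main question.

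The core rests on the text and on the identity in step 1, and needs no assumed figure. The absence of a formula is subject to the one figure not shown. The simulated powers and biases illustrate what follows under assumed spaces and SDs and are not evidence from the documents. It would be too strong to say that the trial cannot show which arm is faster: it can, from models already planned. Raising 10 to 15 per group leaves room for (15 − 10)/15 = one third to leave, but the plan states no drop-out rate, so that is an allowance and not a forecast. Anyone who leaves before closure would have no T1, and so no primary value under the literal rule.

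**What to change.** - **Outcomes section.** Limit the T0–T1 sentence to the secondary outcomes measured on before-and-after models or cephalograms, in line with III) A]. Exclude pain. Align the final-model sentence under Retraction records.
- **Primary outcome.** Define one value per patient in mm per 4 weeks: the slope of remaining extraction space over the existing 4-weekly models, using actual visit dates and only models in which space is still open. If closure comes by the first visit, use distance over elapsed time. Patients without a T1 then still contribute.
- **Distance.** Use space closure in the outcome table, Outcomes, III) A] and III) C]. Report anterior segment movement separately.
- **Analysis.** Compare arms with an independent-samples t-test. Keep the paired test for pre-post change within an arm. State what the ANOVA is for or remove it.
- **Sample size.** State the unit and response variable of 1.0 and 0.76. If they are not mm per 4 weeks, say that the 80% power does not refer to the primary rate.

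Cost: text edits and slightly more analysis work, with no new visits, models or radiographs. There are two downsides. The slope rests on few models in patients who close quickly, and the power basis may have to be restated.

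### No serial order or draw record is described for the allocation envelopes, and the unblinded operator assigns the arm from the code list, so a redraw or misdecoding would be hard to detect

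*Combined protocol and SAP*

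**What the plan says.** The procedure is spread over five places in the protocol.

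- **Sequence generation.** The supervisor lists patient numbers in Excel, attaches a RAND() value to each and sorts: "These numbers will be sorted according to the randomization number so the first column numbers will be randomly distributed". The rule that turns the sorted list into arm A or arm B is not given.
- **Allocation concealment mechanism.** The supervisor will "write the randomization numbers of the patients on opaque white papers folded three times to form sealed envelopes", kept in a box. "The codes for randomization will be securely held" at the secretary's office.
- **Implementation.** The operator sends the patient to that office, where "the assigned employee will open the box and ask the patient to select one envelope". Then: "The main operator will assign each participant for the corresponding intervention either (friction or frictionless group) according to the list of codes of randomization".
- **Blinding.** Operators cannot be blinded. The principal operator is responsible for assigning patients, in line with what the section calls a concealed allocation. Only the outcome assessors are blind.
- **Participant timeline, item 5, and Recruitment strategy.** Item 5 says: "The principle investigator will randomly allocate the patients to one of the intervention groups". Recruitment strategy says: "The principal investigator will recruit the patients from the clinic of Orthodontic department".

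The Auditing section adds that the supervisor will periodically review trial progress, including how patients are allocated to groups.

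**The concern.** Allocation concealment rests on two things: nobody who enrols or treats patients can influence which arm comes next, and a later reader can confirm that the assignments made were those generated. The second is weak here. A patient may take any paper, so no assignment has an expected position in a sequence. The paper has to be decoded, and the person named for that step is the unblinded operator. Nothing in the text says that a paper is tied to a patient before it is opened, or when and under whose control the operator sees the list.

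This matters more than it would in a double-blind trial. Patients and operators know the arm, and the introduction assumes that loops should retract faster. With 15 patients per group, a small number of irregular assignments could affect the comparison, and the plan describes no record from which they could be found.

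**Working it through.** This is a question of procedure. The plan gives no figure for it, so the main check is to set the steps side by side.

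**1. What each step secures**

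| Step | Who acts | Described safeguard | What is not described |
|---|---|---|---|
| Generate list | Supervisor | RAND() sort, separate from the operator | Rule from sorted list to arm |
| Prepare papers | Supervisor | Opaque, folded, described as sealed, each carrying a number | Serial number on the outside; box contents |
| Choose paper | Patient, with an employee opening the box | Operator does not choose | Opening order; patient ID written before opening; whether a paper can go back |
| Decode to arm | Main operator | Codes kept at the secretary's office | When, and under whose control, the operator sees the list |
| Check afterwards | Supervisor (Auditing) | Periodic review of allocation | Any draw record to review against |

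**2. Is the draw random?** Assume 30 papers, 15 per arm, drawn unseen and not returned (the box contents are not stated). Every arm order is then equally likely, with C(30,15) = 155,117,520 possibilities. The split is always 15:15, and the order matches the generated list with probability 1/155,117,520, about 6 × 10⁻⁹. So the draw replaces the list's order, but with another random order. Losing the list's order does not in itself introduce bias; it removes the reference for checking order.

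If instead each patient were allocated independently at 50:50, an exact 15:15 split would occur with probability C(30,15)/2³⁰ = 0.144, and a split of 18:12 or worse with probability 0.362. The text does not say which scheme applies, although the design section states a 1:1 ratio.

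**3. Where could an assignment go wrong?** Before the draw, seeing the code list does not reveal which paper a patient will pick. The exposure comes after the draw: a paper returned and another taken, or a number read to the wrong arm. Neither would conflict with any record the protocol describes.

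**4. Who assigns?** Implementation and Blinding name the main or principal operator; Participant timeline item 5 names the principal investigator. The two are probably one person. The Blinding section gives impressions and casts to the operator, Data collection gives the monthly study models to the principal investigator, and the Declaration of interests describes a self-funded Master's project. No sentence says so.

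**5. Size.** Nothing in the documents supports an estimate. A purely hypothetical illustration: suppose k patients in each arm were steered, those in one arm 1 SD better and those in the other 1 SD worse than an exchangeable patient. With the sample size section's SD of 0.76 and 15 per arm, the shift is 2 × (k/15) × 0.76.

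- k = 1 (2 of 30 patients): 0.10
- k = 2 (4 of 30): 0.20
- k = 3 (6 of 30): 0.30

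The planned difference is 1.0. Both k and the 1 SD effect are invented, and the section does not say which outcome or unit the 0.76 describes.

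**The case against.** The strongest defence is that the procedure already separates the roles. The supervisor generates the list and prepares the papers, the codes sit at the secretary's office, an employee opens the box, and the patient draws. Consent and enrolment (Participant timeline items 3 and 4) come before allocation (item 5), so the recruiter has little scope to choose whom to enrol in light of the next arm. Looking up a drawn number in a code list is a coherent use of that list. The sentence about the operator may mean only that the operator delivers the arm the list shows. The supervisor also reviews allocation.

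Most of this stands, and it rules out several stronger readings that a reader might infer:

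- *The trial is not properly randomised because the sequence is abandoned.* Not supported: an unseen draw without replacement is random.
- *The papers are unnumbered.* Not so: each carries a randomization number. What is missing is a serial number on the outside and an opening order.
- *The recruiter decides the arm.* That recruiter and operator are the same person is a reasonable inference, not a statement.
- *The result could be biased by 10% to 30% of the planned difference.* Those figures only restate assumptions.

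The defence does not supply a record. Audit is useful only against something written down when the patient was allocated, and none is described. Nor does it settle who handles the code list: custody at the secretary's office and assignment from the list by the operator are both stated, with nothing to connect them.

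**Conclusion.** The point holds as a weakness in auditability and role separation. As written, a redraw or misdecoding would be hard to detect, the operator's access to the codes is not controlled, and the Participant timeline and Implementation sections name different people for allocation. It does not show that the allocation is non-random, that anyone can foresee the next arm, or that bias has occurred.

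No size can be attached from the documents. The conclusion rests on two readings: that assigning from the code list means the operator does the decoding, which is the more natural reading but not the only one; and that no serial order or draw record exists because none is described. If local practice already includes them, the remedy reduces to writing them down. The change is worth making because it is inexpensive and because the missing record cannot be recreated once patients have been allocated.

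**What to change.** Replace the draw-and-decode steps with the following.

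1. The supervisor states the rule from sorted list to arm, then places the arm itself inside opaque, sealed envelopes numbered serially on the outside, 1 to 30, in the generated order.
2. Once eligibility and signed consent are logged, the secretary's office writes the patient ID and date on the next unopened envelope, opens it in strict order, records it, and tells the operator the arm.
3. The code list stays with the supervisor or the secretary's office, and the operator never handles it. This must accompany step 1: with serial envelopes, anyone who has seen the list would know the next arm.
4. Delete the patient-selects step and the assignment of arms by the operator from the list. Align Participant timeline item 5 and the Blinding section, so that the operator receives and applies the allocation but does not make it.
5. Name the envelope log as the record that the supervisor checks under Auditing.

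The cost is protocol wording, numbered envelopes and a one-page log, with the same supervisor and secretary's office and no extra patients. If the protocol is already approved, the change goes through its own amendment procedure.
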